6.1. Design Overview

The VItamin C, Thiamine And Steroids in Sepsis (VICTAS) Study is a double-blind, placebo-controlled, adaptive randomized clinical trial designed to investigate the efficacy of the combined use of vitamin C, thiamine and corticosteroids (hereafter "Treatment Protocol" or "TP") versus indistinguishable placebos (hereafter "Control Protocol" or "CP") for patients with sepsis. The trial employs a novel endpoint that approximates a patient's risk of death based on the time spent on vasopressors or receiving respiratory support. Time spent on vasopressors or receiving respiratory support captures a patient's speed of recovery. Mortality rate is a key secondary endpoint for the trial.

The trial has a flexible sample size that will be determined adaptively. The trial will have an initial enrollment target of up to 500 subjects to detect a potential mortality difference of 20%, a conservative estimate based on the 32% benefit observed in the study by Marik, et al. However, if the data are indeterminate on mortality at N=200, 300, or 400 subjects, the trial may continue to a larger sample size (up to 2000) using an adaptive "Goldilocks" strategy based on the primary endpoint of VVFD with assessments at 500, 1000, 1500, or 2000 subjects randomized to either the TP or CP. The overall type I error rate for the trial is controlled at 2.5%. The early interim analyses have conservative rules for spending alpha so that 0.1% will be used up to N=400 and the remaining 2.4% is reserved for N=500 (or beyond). For more detail, please see section on Statistical Considerations below (Section 11).

6.2. Interim Analyses and Criteria for Study Termination

Early interim analyses focused on detection of a large mortality effect will be conducted as soon as possible following the enrollment of subject numbers 200, 300, and 400. At each of these points, predictive probability of meeting significance on the endpoint of mortality once all currently enrolled subjects have been followed to their final outcome will be calculated. If predictive probability of achieving statistical significance (with one-sided alpha set at 0.001) exceeds 90%, study accrual will be stopped. All currently enrolled subjects will continue and the final analysis will be conducted after all currently enrolled subjects have been followed to their final outcome.

If these conditions are not met, the trial will continue under an adaptive "Goldilocks" strategy with a primary endpoint of VVFD. Interim analyses under this design will be performed as soon as possible following the enrollment of subject numbers 500, 1000 and 1500. Following each of these interim analyses, any one of the following actions may result:

- a. Stoppage of the trial for futility on VVFD (6.2.a)
- b. Stoppage of accrual for expected success on VVFD and mortality (6.2.b)
- c. Stoppage of accrual for expected success on VVFD alone (6.2c)
- d. Continuation to the next analysis (6.2.d)

The decision criteria are based on predictive probabilities of meeting statistical significance on VVFD or mortality. Thus, we compute the predictive probability that VVFD (and mortality) will meet statistical significance once all currently enrolled subjects have been followed to their final outcome (30 days after

enrollment). We also compute the predictive probability that VVFD (and mortality) will be significant if the trial continues to its maximum sample size of N=2000. Each of the possible interim actions is described in greater detail below.

a.) Stoppage of the trial for futility

Stoppage of the trial for futility will occur if there is less than 10% predictive probability of ever detecting a statistically significant (alpha = 0.022) beneficial effect on VVFD, even if enrollment continues to 2000 subjects.

b.) Stoppage of accrual for expected success on both VVFD and mortality.

Accrual to the trial may stop for expected success on both the primary endpoint of VVFD and mortality. This requires that predictive probability be greater than 95% for detection of a statistically significant beneficial effect on both VVFD (alpha = 0.022) and mortality (alpha = 0.024) at the current sample size. In order to meet this threshold, the data must already be strongly positive, and furthermore, there must be little risk that the subjects with outstanding data might reverse the success once all data becomes available. If this threshold is reached, then no additional subjects will be enrolled. Follow-up of currently enrolled subjects will continue and the final analysis will be conducted after all currently enrolled subjects have been followed to their final outcome.

c.) Stoppage of accrual for expected success on VVFD alone

Accrual to the trial may also stop for expected success on the primary endpoint of VVFD alone. This requires that predictive probability for detecting a statistically significant beneficial effect (at the current sample size) on VVFD exceeds 95% and predictive probability for detection of such an effect on mortality (at the maximal sample size) is less than 10%. Thus, the data must already be strongly positive for VVFD and indicate a low probability that significance can be achieved on mortality, even with additional sample size. If this early stopping threshold is reached, then no additional subjects will be enrolled. Follow-up of currently enrolled subjects will continue and the final analysis will be conducted after all currently enrolled subjects have been followed to their final outcome.

d.) Continue to the next analysis

If no condition for stopping accrual is met at the interim, then the trial will continue accrual to the next analysis time (either the next scheduled interim, or to full enrollment and final analysis). For more detail, please see section on Statistical Considerations below (Section 11).

6.3. Number of Subjects

There is an initial enrollment target of 500 subjects, with a maximum of 2000 subjects to be enrolled in the VICTAS Trial. Subjects will be randomized to study invention or control in 1:1 fashion. *A priori* stoppage rules will determine final number of subjects enrolled based on the adaptive study design.

6.4. Study Initiation and Expected Trial Duration

The VICTAS Study is expected to begin enrollment in the spring of 2018. Enrollment of 500 subjects is predicted to require approximately 36 months after the first subject is enrolled. A minimum of 20 sites will participate in subject recruitment and enrollment.

7. Study Population

Any patients admitted to a study site hospital who have or subsequently develop sepsis or septic shock associated with cardiovascular or respiratory failure will be considered for enrollment. The site is responsible for screening patients and selecting those who are appropriate for the study based on the defined inclusion and exclusion criteria (section 7.1). Subjects must be randomized within 24 hours of the onset of organ failure (i.e., cardiovascular or respiratory support).

7.1. Inclusion Criteria

- a) Suspected or confirmed infection as evidenced by ordering of blood cultures and administration of at least one antimicrobial agent
- b) Anticipated or confirmed intensive care unit (ICU) admission
- c) Acute respiratory and/or cardiovascular organ dysfunction attributed to sepsis as evidenced by at least one of the following requirements:
 - Respiratory Support Requirement Acute hypoxemic respiratory failure defined as persistent hypoxemia (PaO₂/FiO₂ ≤ 300 or SpO₂/FiO₂ ≤ 315) requiring (1) intubation and mechanical ventilation, or (2) positive pressure ventilation via tight-fitting face mask (i.e. CPAP or BIPAP) or (3) high flow nasal cannula ≥ 40 LPM flow and FiO2 ≥ 0.40
 - 2. Vasopressor Requirement Continuous infusion of norepinephrine, epinephrine, vasopressin, dopamine, phenylephrine or other vasopressor agents at any dose for greater than 1 hour and required to maintain a mean arterial pressure ≥ 65 mm Hg despite intravenous crystalloid infusion of at least 1000cc
- 7.2. Exclusion Criteria
 - a) Age < 18 years of age
 - b) Weight < 40 kg
 - c) Prior enrollment in VICTAS
 - d) Qualifying organ dysfunction no longer present at the time subject would be randomized (does not require either (1) respiratory support as defined above to maintain $PaO_2/FiO_2 > 300$ or $SpO_2/FiO_2 > 315$ or (2) vasopressor infusion to maintain a mean arterial pressure ≥ 65 mm Hg)
 - e) Cardiovascular or respiratory organ failure caused by an illness other than sepsis
 - f) First episode of qualifying organ dysfunction during the current ED or ICU admission occurred > 24 hours before subject could be randomized (patients may be reconsidered for enrollment during a subsequent ED or ICU admission)
 - g) Limitations of care (defined as refusal of cardiovascular and respiratory support modes described in inclusion criteria 7.1.b) including "do not intubate" (DNI) status
 - h) Current hospitalization > 30 days at time of randomization

- i) Chronic hypoxemia requiring supplemental non-invasive oxygen (nasal cannula or NIPPV) or home mechanical ventilation
- j) Chronic cardiovascular failure requiring home mechanical hemodynamic support (e.g., LVAD) or home chemical hemodynamic support (e.g., milrinone)
- k) Known allergy or known contraindication to vitamin C, thiamine, or corticosteroids (including previous history or active diagnosis of primary hyperoxaluria and/or oxalate nephropathy, or known/suspected ethylene glycol ingestion, or known G6PD Deficiency)
- Use of vitamin C at a dose of > 1g/day (IV or oral) within the 24 hours preceding first episode of qualifying organ dysfunction during a given ED or ICU admission
- m) Chronic disease/illness that, in the opinion of the site investigator, have an expected lifespan of < 30 days unrelated to current sepsis diagnosis (e.g., stage IV malignancy, neurodegenerative disease, etc.)
- n) Pregnancy or known active breastfeeding
- o) Prisoner or Incarceration
- p) Current participation in another interventional research study*
- q) Inability or unwillingness of subject or legal surrogate/representative to give written informed consent

*Note: Co-enrollment in other interventional research studies requires written permission from the VICTAS Executive Committee in advance of subject identification.

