- i) Chronic hypoxemia requiring supplemental non-invasive oxygen (nasal cannula or NIPPV) or home mechanical ventilation
- j) Chronic cardiovascular failure requiring home mechanical hemodynamic support (e.g., LVAD) or home chemical hemodynamic support (e.g., milrinone)
- k) Known allergy or known contraindication to vitamin C, thiamine, or corticosteroids (including previous history or active diagnosis of primary hyperoxaluria and/or oxalate nephropathy, or known/suspected ethylene glycol ingestion, or known G6PD Deficiency)
- 1) Use of vitamin C at a dose of $\geq 1g/day$ (IV or oral) within the 24 hours preceding first episode of qualifying organ dysfunction during a given ED or ICU admission
- m) Chronic disease/illness that, in the opinion of the site investigator, have an expected lifespan of < 30 days unrelated to current sepsis diagnosis (e.g., stage IV malignancy, neurodegenerative disease, etc.)
- n) Pregnancy or known active breastfeeding
- o) Prisoner or Incarceration
- p) Current participation in another interventional research study* Inability or unwillingness of subject or legal surrogate/representative to give written informed consent

*Note: Co-enrollment in other interventional research studies requires written permission from the VICTAS Executive Committee in advance of subject identification.

Study Endpoints (Outcome Variables)

Primary Outcome: Vasopressor and ventilator-free days (VVFD) Secondary Outcomes:

- 1. Mortality at 30 days
- 2. ICU mortality

- 3. Mortality at 180 days
- 3. Length of ICU stay
- 4. Length of hospital stay
- 5. Physical, emotional and cognitive outcomes at 180 days

Statistical Considerations

- 1. An initial target of up to 500 subjects will be enrolled in the VICTAS Study. Subjects will be randomized to study invention or control in 1:1 fashion. A priori stoppage rules will determine final number of subjects (up to 2000) enrolled based on adaptive design.
- 2. All randomized subjects will be included in the ITT analysis set. The ITT population will be used for all primary, secondary, and other efficacy analyses. In these analyses, subjects will be classified according to the treatment randomized (not actual treatment received).

2. Table of Abbreviations

Abbreviation	Text						
ABG	Arterial Blood Gas						
AE	Adverse Event						
AKI	Acute Kidney Injury						
APACHE II	Acute Physiology and Chronic Health Evaluation II						
bCAM	Brief Confusion Assessment Method						

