8.3. Treatment and Study Drug Administration

Randomized subjects will receive either active agents or placebos, labeled as VICTAS Study Drug 1, VICTAS Study Drug 2, and VICTAS Study Drug 3. The table below details these three active agents or matching placebos.

	VICTAS S	Study Drug 1	VICTAS Stu	ıdy Drug 2	VICTAS Study Drug 3			
Intervention	Vitamin C	Placebo	Thiamine	Placebo	Hydrocortisone	Placebo		
Active Agent	Ascorbic acid	N/A	Thiamine hydrochloride	N/A	Hydrocortisone sodium succinate, powder	N/A		
Carrier / Reconstitute	Dextrose 5%	Normal Saline in Dextrose 5%	Monothiol- glycerol, 0.5% v/v; water for injection	Normal Saline	Sterile Water or Normal Saline	Normal Saline		
Strength	25000 mg in 50 ml	N/A	200 mg in 2 mL	N/A	100 mg in 2 mL	N/A		
Dose	1.5 grams	N/A	100 mg	N/A	50 mg	N/A		
Volume and rate to be administered	50 mL over 30 minutes (100 mL/hour)	50 mL over 30 minutes (100 mL/hour)	1 mL over 2-3 minutes	1 mL over 2- 3 minutes	1 mL over 2-3 minutes	1 mL over 2- 3 minutes		
Expiration	24 hours refrigerated and protected from light		24 hours		24 hours			
Route	Intravenous (IV)							
Frequency			Every 6 hours					
Duration	96 hours while physically in the ICU							

Administration – Randomized subjects will receive VICTAS Study Drugs 1, 2, and 3, via intravenous administration every 6 hours up to 96 hours. The first dose should be administered as soon as possible but no longer than 4 hours from randomization. All subsequent doses should default to the local institution every 6 hour routine dosing schedule. All three study drugs should be administered within +/- 2 hours of their scheduled time. Missed doses should be treated via the "Treatment Compliance and Discontinuation" section of this protocol (page 27). All three study drugs should be administered separately and should not be infused or administered with any other medications or study drugs. We recommend that study drugs 2 and 3 be administered first since they are IV push and study drug 1 is administered over 30 mins. *For subjects already prescribed open-label corticosteroids at the time of randomization, or for patients prescribed corticosteroids after randomization, see section below on steroid management.*

The total number of individual study drug administrations is 48 (3 study drugs per administration x 4 administrations per day x 4 days). The total number of study drug administration time points per day is 4 (3 study drugs per administration).

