8.6. Concomitant Therapies

Any patient currently participating in another trial of a pharmacologic agent for sepsis will not be eligible for enrollment in the VICTAS trial. Any patient enrolled in another trial that requires administration of vitamin C, thiamine or hydrocortisone will not be eligible for enrollment in the VICTAS trial.

Subjects may receive Vitamin C, thiamine, or hydrocortisone during the course of the study at the discretion of their treating physicians with the following stipulations:

Vitamin C

- May be given for known or suspected vitamin C deficiency (i.e. scurvy).
- May not be given at doses greater than 1g daily (total daily dose) either orally or intravenously.
- Any administration of vitamin C outside of study protocol will be recorded and registered.

Thiamine

• May be given for known or suspected thiamine deficiency (e.g., prevention of Wernicke's encephalopathy in chronic alcoholics or malnourished patients).

Hydrocortisone

- As detailed previously, the use of hydrocortisone will be allowed at the discretion of the primary clinical teams. Refer to section discussing steroid management for further detail.
- The use of other steroid agents will be allowed, and will be converted to hydrocortisone equivalent doses for the purposes of determining the details of Study Drug 3 (see APPENDIX A). Subjects on chronic steroids will not be excluded from enrollment.
- 8.7. Drug Storage, Accounting and Disposal

[figure not shown]
Storage – All study drugs will be stored on site and are expected to remain stable for months under the pre-specified temperature control. Expiration dates and shelf life for study drugs will be determined and amended based on stability testing. Study drug(s) will be sent to sites prior to the expiration dates.

[figure not shown]
Accountability – The CCC and Central Pharmacy will provide management of ensuring appropriate amount of study drug is at each site. Sites will maintain appropriate and accurate drug accountability.

Drug Disposal – Any expired drug kits must be destroyed per the institutions disposal policies and documented on the accountability record. Study drugs that are administered and have left over product requiring wasting do not require documentation on the accountability record.

9. Study Screening and Enrollment

9.1. Study and Subject Progression Flow Chart The diagram below illustrates the screening and enrollment process for the trial.

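### The vitamin C exclusion stops at the onset of organ dysfunction, so high-dose vitamin C ordered clinically between onset and randomization neither excludes a patient nor removes the patient from the per-protocol set (minor)

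*Combined protocol and SAP*

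**What the plan says.** Three rules bear on vitamin C given outside the study regimen.

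- **Eligibility, section 7.2(l).** The body text excludes patients who used vitamin C above 1 g/day, by either route, "within the 24 hours preceding first episode of qualifying organ dysfunction during a given ED or ICU admission". The same item in the executive summary uses the same time anchor: "IV or oral) within the 24 hours preceding first episode of qualifying organ dysfunction during a given ED or ICU admission".
- **Time to randomization, sections 7 and 7.2(f).** A patient is excluded if "First episode of qualifying organ dysfunction during the current ED or ICU admission occurred > 24 hours before subject could be randomized". The opening of section 7 agrees: "Subjects must be randomized within 24 hours of the onset of organ failure". So up to 24 hours may pass between onset and randomization.
- **Conduct, section 8.6.** For subjects in the course of the study, vitamin C is limited: "May not be given at doses greater than 1g daily (total daily dose) either orally or intravenously". Off-protocol vitamin C is to be recorded. Under sections 9.3 and 12.3 a patient counts as enrolled only once consent is given and the randomization code is issued.

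Two provisions give partial cover. Exclusion (p) rules out patients in other interventional studies unless permission is given in advance, and section 8.6 rules out patients in another trial that requires vitamin C.

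Section 11.3.2 admits a patient to the per-protocol set if all inclusion criteria and no exclusion criteria are met, subject to a minimum number of doses and no major deviations.

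**The concern.** Exclusion (l) and the 8.6 limit appear to share one aim: to keep vitamin C above about 1 g/day from confusing the comparison. Exclusion (l) looks back from onset and 8.6 looks forward from enrollment. The time between them is when a clinician treating new shock or respiratory failure would be most likely to start vitamin C for the sepsis itself. As written, a patient who took oral vitamin C above the limit the day before shock is excluded, while one given intravenous vitamin C at the trial dose some hours after shock is not.

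The documents give no reason for anchoring (l) at onset, and it is not a general convention: exclusions (d) and (h) are anchored at randomization.

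At stake is the vitamin C contrast in the affected patients. A control patient may already have received some of the active agent, and the per-protocol sensitivity analysis would keep that patient.

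**Working it through.** The plan states no figure on this point, so there is none to reproduce. The check sets the time windows side by side and then bounds the size.

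**1. Time line.** Put first qualifying organ dysfunction at hour 0 and randomization at hour R, with 0 ≤ R ≤ 24 (sections 7 and 7.2(f)).

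| Interval | Rule that limits clinically ordered vitamin C |
|---|---|
| −24 h to 0 | Exclusion (l) |
| 0 to R | None |
| R onward | Section 8.6 limit |

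The uncovered interval has length R, anywhere from 0 to 24 h. Section 8.3 says of study drug: "The first dose should be administered as soon as possible but no longer than 4 hours from randomization". First study dose can therefore fall at up to 24 + 4 = 28 h after onset, but those last 4 h come after randomization, under 8.6.

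**2. Largest exposure on the trial's own schedule** (1.5 g every 6 h, section 8.1).

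- Doses in 24 h: 24 / 6 = 4, giving 4 × 1.5 g = 6 g.
- Full study course: 4 per day × 4 days = 16 doses, giving 16 × 1.5 g = 24 g.
- Share of a course: 6 / 24 = 25%.

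This is a maximum. It needs treatment to start within hours of onset and randomization to come late.

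**3. An example that holds on either reading of onset.** The vasopressor criterion requires infusion for more than 1 hour, so onset could be read as the start of infusion or as the moment that hour is passed. Suppose the infusion starts at hour 0, vitamin C 1.5 g is given at hours 4, 10, 16 and 22, and randomization is at hour 23. On both readings every dose follows onset and randomization is within 24 h. The patient receives 6 g without meeting exclusion (l).

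**4. Per-protocol set.** This patient breaks no exclusion, so the eligibility condition in 11.3.2 does not remove the patient. If the open-label order ran on past randomization above the 8.6 limit, that would be a deviation and might lead to removal. Exposure confined to the interval before randomization would not.

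**5. Effect on the contrast.** If the same 4 pre-doses are given in both arms, a treated patient totals 4 + 16 = 20 doses and a control 4 + 0 = 4. The difference is 16 doses, the same as with no pre-exposure. The contrast in outcome shrinks only if early doses carry a disproportionate share of the benefit or the benefit saturates.

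**6. Size under assumption.** Let p be the share of patients exposed and f the share of the effect lost in them; overall attenuation is p × f. The documents give no p. Taking 2% to 10% purely as an illustrative range:

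- f = 0.25 (the share of a course): 0.25 × 2% = 0.5% to 0.25 × 10% = 2.5%.
- f = 1 (no contrast left, an extreme bound because only one of three agents is involved): 2% to 10%. The approximate sample-size inflation 1/(1 − p)² is 1/0.98² = 1.04 to 1/0.90² = 1.23.

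The upper end of p sits badly with section 3.4, which reports the combination as seldom or never used.

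**The case against.** The case against giving this weight is strong.

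- **Frequency.** The only evidence in the documents, the informal survey in section 3.4, points to very little use. Vitamin C given inside another trial is already dealt with. *This stands*, and it limits the point to a minor one. The survey is described as non-scientific and gives no rate.
- **Balance.** Exposure before randomization is a baseline characteristic, balanced in expectation. A reader might infer that pre-treatment necessarily shrinks the treatment contrast or distorts the error rate. The documents support neither: the dose difference is unchanged (step 5), and under no treatment effect the arms remain comparable. *This stands.* Dilution requires early or saturable benefit. That is not far-fetched, since section 8.2 rests the dose partly on rapid repletion, but it is an assumption.
- **Baseline samples.** A reader might infer that the section 10.7 baseline is spoiled. Those samples are taken at select sites, are optional for subjects, and measure ascorbate directly before study drug, so pre-loading would be seen. The criterion already admits lower-dose users, so an untreated baseline was never assured. *This stands.*
- **Design choice.** The trial tolerates open-label corticosteroids, chronic steroid use and thiamine without a dose limit. *This stands only in part*: vitamin C is the one component given both a prior-use exclusion and a daily limit, so the plan does mean to control it.
- **Threshold sign.** The executive summary prints a greater-than-or-equal sign and section 7.2 a greater-than sign. A reader might call this a contradiction. Text extraction may have lost a symbol, so it should be checked in the source PDF and is not counted here as an error.

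**Conclusion.** The gap is real on the plain text. Between onset and randomization, for up to 24 hours, no rule covers clinically ordered vitamin C above the threshold, and the per-protocol eligibility condition does not pick it up. The most that fits on the trial's schedule is 4 doses, or 6 g.

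The consequence is small. It rests on an unknown but probably low frequency of use, and on a benefit that is early or saturable; without the second condition the contrast is not reduced at all. Any dilution would make the trial slightly conservative. The thresholds for the rank-sum and chi-square tests are unaffected.

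The documents do not support a claim that a material share of patients is affected: the percentages in step 6 are assumptions for scale, not estimates. This is a minor point, raised because the correction is cheap.

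**What to change.** In section 7.2(l) and in item (l) of the executive summary, extend the existing look-back so that it runs from 24 hours before the first qualifying organ dysfunction up to randomization. Keep the sponsor's own threshold, check its symbol against the source PDF so that both places match, and reconcile its wording with the limit in section 8.6. No view is taken here on what the threshold should be.

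No separate data item is needed for eligibility, because section 9.2 already requires the eligibility form to confirm every criterion; the form's wording need only follow the revised text. Patients who break the revised criterion would then also fall outside the per-protocol set without any change to 11.3.2.

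The cost is a short wording amendment, plus a very small number of patients who become ineligible because they were already treated. That cost and the benefit both scale with how often such use occurs.
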